13.2 Primary/Secondary Endpoints/Hypotheses and Analytical Methods

Descriptive statistics will be performed for baseline data, and distributions of outcome measures will be characterized using scatterplots, histograms, and summary statistics (e.g., mean, median, standard deviation, quartiles, range) to identify extreme outliers. Outcome variables will be log-transformed if their distributions are not symmetric. We will also examine if these measurements are balanced between the study intervention groups. The primary assessment of the exercise intervention effects will compare the average change from baseline to 24-week follow-up outcome measures (such as SF-36 physical component score) between the exercise group and the control group. Analyses will be intention-to-treat. The generalized estimating equations (GEE) modification of linear regression will be used in order to model the relationship between the outcome measures and exercise intervention and to account for the correlation within individual data over time. The GEE model will adjust for the measurement time and other potential covariates. Prior to fitting the GEE model, logarithmic transformation will be applied (if appropriate) to the outcome data to achieve approximate normality and variance stabilization. Our statistical inference on each outcome will use the standard large-sample approximation, namely, two-sided Z-test and Z-confidence intervals based on the limiting Gaussian distribution. More specifically, for the primary comparison between exercise group *vs.* control group, let Y_{ij} be the outcome measure (or log-transformed if appropriate) of interest for participant i at time j , where j is 0 for baseline and 1 for 24 week follow-up, X_i be the indicator variable for the intervention status (1=intervention, 0=control) and Z_i represent a vector of other potential adjusting variables (such as age, BMI). The linear model is as follows:

$$E[Y_{ij}] = \alpha_0 + \alpha_1 j + \beta_0 X_i + \beta_1 X_i j + \gamma^T Z_i, \text{Var}[Y_{ij}] = \sigma^2 \text{ and } \text{Cov}[Y_{ij}, Y_{kl}] = \rho \text{ if } i = k \text{ and } j \neq l, \text{ and } 0 \text{ otherwise.}$$

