The parameter β_1 is of our main interest and represents the mean difference in the outcome change from baseline to follow-up between participants in the exercise group and participants in the control group, adjusting for covariates Z such as age and BMI. We will first assess β_1 without any adjustments for Z (unadjusted analysis), and then add Z (adjusted analysis). Under the null hypothesis of no difference between intervention and control on the changes in the outcome measure, β_1 is equal to zero. If the exercise intervention indeed results in a greater reduction/increase in the outcome measure of interest in the exercise group compared with the control group, then β_1 is different from zero. Our statistical inference on β_1 will use the standard large-sample approximation, namely, two-sided Z-test and Z-confidence intervals based on the limiting Gaussian distribution.

Our analysis will be based primarily on intention-to-treat principle, but with minor modifications for practical considerations. The principles of ITT analyses are (i) keep participants in the intervention groups to which they were randomized, regardless of the intervention they actually received; (ii) measure outcome data on all participants; and (iii) include all randomized participants in the analysis (107). However, if data of individuals are lost, or are unavailable for other reasons immediately after randomization, then we will not include these individuals in the analysis (modified intention-to-treat). Under the modified intention-to-treat principle, enrolled participants who were later found to be ineligible will not be included in the primary analysis. To take adherence into account, we will also perform per-protocol analysis which includes only individuals who are considered adherent to the intervention assignment. Per-protocol analysis will not be our primary analysis, and we will report in detail the criteria for exclusion of individuals.

If we encounter missing data due to drop out or assay issues, we will apply mixed model regression using the available data in the analysis. In general, our analysis based on available data will be similar to the analysis using the individuals who do not have missing data (complete-case analysis) if the missing data mechanism is completely at random (108). When the

Protocol 10045

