13.3 Sample Size and Power

98 individuals will be randomized. Accounting for up to 20% drop-out, power calculations are based on 78 participants.

Table 1. Minimum detectable absolute difference in mean change from baseline to 24 weeks between two groups (n=39 for Control group and n=39 for Exercise group) for the study endpoints, given an intra-individual correlation (ρ) of 0.5, 0.65 or 0.8, at 80% power, and adjusting for the number of hypotheses tests with 7 primary endpoints (type I error of 0.05/7).

Endpoint	Mean	SD	Minimum detectable absolute difference (% change)		
			$\rho = 0.5$	$\rho = 0.65$	$\rho = 0.8$
Distress (Perceived Stress Scale) ^a	19.23	6.77	5.41 (28.16%)	4.53 (23.56%)	3.42 (17.81%)
Distress (Hospital Anxiety and Depression Scale-anxiety subscale) ^b	7.4	3.9	3.12 (42.15%)	2.61 (35.27%)	1.97 (26.66%)
Distress (Hospital Anxiety and Depression Scale-depression subscale) ^b	5.8	3.5	2.87 (48.26%)	2.346 (40.4%)	1.77 (30.52%)
Quality of Life (36-item Short Form Survey- Physical Component Score) ^c	45.6	9.2	7.36 (16.14%)	6.16 (13.5%)	4.65 (10.21%)
IL-6 (pg/mL) ^d	2	0.7	0.56 (27.99%)	0.47(23.42%)	0.35 (17.70%)
VEGF (pg/mL) ^e	192	158.2	126.5 (65.88%)	105.8 (55.12%)	80(41.67%)
Salivary cortisol (nmol/L) ^d	4	0.6	0.48 (12.0%)	0.4 (10.04%)	0.3 (7.59%)

Mean and SD obtained from: ^a Perceived Stress Scale score in ovarian cancer survivors at the end of primary chemotherapy (111), ^b Hospital Anxiety and Depression Scale anxiety and depression subscale scores in ovarian cancer survivors towards end of primary chemotherapy (112), ^c 36-item Short Form Survey- Physical Component Score in our randomized controlled trial of exercise in ovarian cancer survivors (17), ^d biomarker levels in ovarian cancer survivors 6 months after primary treatment(113), and ^e VEGF levels in ovarian cancer survivors after completion of primary chemotherapy (114).

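### Adding age and BMI as planned leaves the primary effect unchanged when pairs are complete; conditioning on the baseline outcome would sharpen every primary comparison at no data cost

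*Combined protocol and SAP*

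**What the plan says.** Section 13.2 states that the primary assessment "will compare the average change from baseline to 24-week follow-up outcome measures" between the arms. The baseline value (j = 0) and the 24-week value (j = 1) are both responses in a GEE linear model, used "to account for the correlation within individual data over time". The mean is α0 + α1·j + β0·X + β1·X·j + γᵀZ, and β1 is the parameter of interest, described as the difference in change between the exercise group and "participants in the control group, adjusting for covariates Z such as age and BMI". The plan lets "Z_i represent a vector of other potential adjusting variables (such as age, BMI" among the examples. Z carries no time index and there is no Z-by-time term. The effect is to be estimated "without any adjustments for Z (unadjusted analysis), and then add Z (adjusted analysis". For drop-out or assay failures, "we will apply mixed model regression using the available data in the analysis".

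Section 13.3 gives the "Minimum detectable absolute difference in mean change from baseline to 24 weeks between two groups" in Table 1, and says: "Accounting for up to 20% drop-out, power calculations are based on 78 participants". Section 13.4 stratifies randomisation by stage (II-IIIA, IIIB-IV) and BMI (below 30, 30 or above). BMI is an example of Z. Stage is neither named nor excluded as a model term.

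**The concern.** Two features of the model leave precision unused.

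- **The adjusted step adds nothing for complete pairs.** A covariate that shifts both of a participant's measurements equally drops out of her change. It can alter β1 only through participants with one measurement missing. A reader of the results could take the second estimate as further evidence when it is largely the first one repeated.
- **The baseline outcome is not a covariate.** Using it only as the j = 0 response amounts, with complete pairs, to fixing its coefficient at 1. Estimating that coefficient is never less efficient in large samples, and it is clearly better at the correlations the plan assumes.

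Precision is scarce here. Seven primary endpoints are each tested at 0.05/7, with 78 completers expected. The earlier exercise trial described in Section 2.3 found SF-36 physical component changes of 1.8 and −2.0, a difference of 3.8. That is below all three detectable differences in Table 1 for this endpoint (7.36, 6.16 and 4.65).

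**Working it through.** **Inputs.** Two-sided Z-test (13.2). Type I error 0.05/7, 80% power, 39 per arm at 24 weeks, ρ = 0.5/0.65/0.8, and the SDs in Table 1 (13.3). 49 randomised per arm (13.4). Critical values: 2.690 + 0.842 = 3.532.

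**Step 1: reproduce Table 1.** Detectable difference = 3.532 × SD × √[2(1−ρ)] × √(2/39). For the Perceived Stress Scale (SD 6.77) at ρ = 0.5 this is 3.532 × 6.77 × 1 × 0.2265 = 5.41, as printed. The formula reproduces 20 of the 21 absolute entries to rounding. The exception is HADS depression at ρ = 0.5, printed as 2.87. The formula gives 2.80, and so does the printed percentage (48.26% of 5.8), so this looks like a misprint. Table 1 is therefore the unadjusted change-score comparison.

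**Step 2: why Z cancels.** For a complete pair, take the difference and the sum of the two values.

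- The difference has mean α1 + β1·X, with no Z in it.
- The sum contains Z, but its arm coefficient is 2β0 + β1. Because β0 is free, the sum says nothing about β1.
- Under the written covariance the sum and difference are uncorrelated, so β1 is the raw difference in mean change.

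A numerical check used simulated data with 78 complete pairs and outcomes that depended on age and BMI. β1 was −0.042012 with and without Z under exchangeable GEE, independence GEE and a mixed model. The robust SE was 0.21192 in both GEE fits, with and without Z. β1 moved only when an age-by-time term was added (−0.0251) or when 16 of the 78 follow-up values were removed (−0.149 without Z, −0.178 with Z). In 800 simulated trials with 20 of 98 follow-ups missing, and Z assumed to explain 20% of the variance, the mean shift in β1 was 0.018/0.012/0.008 SD and the largest 0.089 SD.

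**Step 3: condition on baseline, complete pairs.** The variance factor 2(1−ρ) becomes 1−ρ², so the ratio of detectable differences is √[(1+ρ)/2] = 0.866/0.908/0.949. That is a cut of 13.4/9.2/5.1%. Estimating the slope multiplies the SE by about √(1 + 1/74) = 1.0067, which leaves 12.8/8.6/4.5%.

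Before the slope cost, at ρ = 0.5/0.65/0.8:

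| Endpoint | Change score (Table 1 formula) | Conditioned on baseline |
|---|---|---|
| Perceived Stress Scale | 5.41 / 4.53 / 3.42 | 4.69 / 4.11 / 3.25 |
| HADS anxiety | 3.12 / 2.61 / 1.97 | 2.70 / 2.37 / 1.87 |
| HADS depression | 2.80 / 2.34 / 1.77 | 2.42 / 2.13 / 1.68 |
| SF-36 physical component | 7.36 / 6.16 / 4.65 | 6.37 / 5.59 / 4.41 |
| IL-6 | 0.560 / 0.468 / 0.354 | 0.485 / 0.425 / 0.336 |
| VEGF | 126.5 / 105.9 / 80.0 | 109.6 / 96.2 / 75.9 |
| Salivary cortisol | 0.480 / 0.401 / 0.303 | 0.416 / 0.365 / 0.288 |

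**Step 4: planned drop-out.** With 49 baselines and 39 follow-ups per arm, missing completely at random, the variance of β1 in SD² units is:

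- written model: 2[(1−ρ²)/39 + (1−ρ)²/49], giving SE 0.2206/0.1861/0.1418;
- conditioned on baseline: 2(1−ρ²)/39, giving SE 0.1961/0.1721/0.1359.

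The cut is 11.1/7.5/4.1%, or 10.5/6.9/3.5% with the slope cost. For the Perceived Stress Scale, 5.27/4.45/3.39 becomes 4.69/4.11/3.25 before the slope cost and 4.72/4.14/3.27 after it.

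**Step 5: power at Table 1's own differences.** The change score on complete pairs has 80% by construction. The written model at planned drop-out has 82.5/81.8/81.0%. Conditioning on baseline gives about 91/88/84% with the slope cost.

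**Step 6: simulation at planned drop-out** (4,000 trials per ρ, 98 randomised, 20% missing at 24 weeks):

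| Model | Empirical SE |
|---|---|
| Written model | 0.223 / 0.186 / 0.141 |
| 24-week value regressed on arm and baseline | 0.198 / 0.174 / 0.137 |
| Common baseline mean, exchangeable | 0.198 / 0.173 / 0.137 |
| Common baseline mean, independence | 0.227 / 0.227 / 0.223 |

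**The case against.** The strongest reply is that nothing is wrong. Change scores and baseline-adjusted regression are both valid, and Table 1 is computed for the planned one. That stands, and it is why this is put as an efficiency improvement.

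Other replies have partial force.

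- **Complete pairs are not what the plan expects.** With up to 20% drop-out, Z can move β1 slightly and the written model already recovers some precision. The fair comparison is therefore 10.5/6.9/3.5%, with power starting from 82.5/81.8/81.0%. At ρ = 0.8 the gain is small, and the documents do not say which ρ applies.
- **The regression on the 24-week value drops participants without one, although the plan wants to use all available data.** True, but Step 6 shows almost no loss of precision against the common-baseline model, which keeps them.
- **The covariance is already specified.** Section 13.2 writes a constant variance and one within-person covariance, which is exchangeable for two time points. The warning about independence applies only to the common-baseline alternative.
- **Z is an open list, so stage could be included.** It could, but it is not pre-specified. No gain is claimed for stage, BMI or age, because the documents give no correlation between them and the outcomes.
- **The biomarkers may be log-transformed.** The raw-unit biomarker figures would then not apply. The percentage cuts would hold for the correlation on the log scale.

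**Conclusion.** The concern holds as a point about efficiency; it alleges no bias, type I error problem or fault in the power calculation. With complete pairs, the planned adjustment for Z leaves β1 unchanged. Conditioning on the baseline outcome would lower detectable differences by 12.8/8.6/4.5% with complete pairs, and by 10.5/6.9/3.5% against the written model at planned drop-out, both net of the slope cost and at ρ = 0.5/0.65/0.8. All of that gain comes from the baseline value. It rests on equal variances at the two times, a linear relation between baseline and 24-week values, a correlation within the plan's own range and, for the drop-out figures, values missing completely at random.

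**What to change.** For each primary endpoint, pre-specify one of two primary models in Section 13.2.

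1. A regression of the 24-week value on arm, the baseline value of that outcome, stage (II-IIIA, IIIB-IV) and BMI (below 30, 30 or above). With baseline in the model, using the change as the response gives the same arm coefficient, so the endpoints in Section 3.3.1 need not change.
2. The longitudinal model with a common baseline mean (β0·X removed), covariate-by-time terms, and an exchangeable or unstructured within-person correlation. This keeps participants who lack a 24-week value. It must not be fitted with an independence working correlation, which in simulation was less precise than the written model at every ρ. The SAP should name the structure for this model explicitly.

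Keep the change-score comparison as a supportive analysis. Show the detectable differences under the adjusted model beside Table 1, and reconcile the HADS depression entry at ρ = 0.5.

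The cost is SAP wording and extra table columns. Baseline assessments and both strata are available before randomisation, so no new data are needed. The statistical cost is about 0.7% in SE for the estimated slope, plus at most 0.4% if the two strata prove unrelated to outcome (simulated under stratified permuted blocks).

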13.4 Randomization

After baseline assessments are complete, participants will be randomized with equal probability to the exercise intervention (N=49) or wait-list control (N=49). Randomization will be blocked on stage (stages II-IIIA vs. IIIB-IV) and body mass index (<30 kg/m² vs. \geq 30 kg/m²) and will use permuted blocks with random size.

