13.5 Additional Efficacy Hypotheses, Outcome Measures, and Statistical Methods

Our exploratory analyses will investigate the effect of the moderate exercise intervention on 24-hour urinary norepinephrine levels. We will use the above GEE model in this investigation to compare the mean changes from baseline to 24-weeks between the exercise intervention and control groups. We will assess the relationships between the change from baseline to 24 weeks in each of the distress or quality of life measures and change from baseline to 24 weeks in each of the biomarkers (IL-6, VEGF, salivary cortisol, urinary norepinephrine) based on the Pearson correlation. Also, we will investigate the association between changes in the outcomes from baseline to 24 weeks (distress, Quality of Life, biomarkers) and exercise adherence among participants in the intervention group. We will provide the mean change in the outcome by category of exercise adherence (\geq 150 min/week, 120-149 min/week, 90-119 min/week, 60-89 min/week, 30-59 min/week, and <30 min/week).

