13.6 Analysis of Covariates

Descriptive statistics will be performed for baseline covariate data, including summary statistics (e.g., mean, median, standard deviation, quartiles, range) to identify extreme outliers. We will examine if covariates are balanced between study groups.

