13.7 Exploratory Analysis

In exploratory subgroup analyses, we will apply the GEE models for the primary analysis given above to study the intervention effect on each of the primary outcomes among participants who developed (versus those who did not develop) recurrence over the course of the study. The GEE models will also be applied to additional exploratory subgroup analyses to assess the intervention effects on the primary outcomes by chemotherapy maintenance group (if the sample size is sufficient).

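### The covariate-adjusted analysis in Section 13.2 barely adjusts the treatment effect, and stage, a randomisation stratum, is named in no model

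*Combined protocol and SAP*

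**What the plan says.** Section 13.2 fits a linear GEE model to two time points, baseline (j = 0) and week 24 (j = 1):

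E[Y_ij] = α0 + α1 j + β0 X_i + β1 X_i j + γ'Z_i.

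X_i is arm. Z_i is said to "represent a vector of other potential adjusting variables (such as age, BMI"). The parameter of interest is β1, the between-arm difference in mean change, which the section describes as adjusted for Z. It is to be estimated first "without any adjustments for Z (unadjusted analysis), and then add Z (adjusted analysis"). For missing data, "we will apply mixed model regression using the available data in the analysis"; imputation, weighting, last observation carried forward and pattern-mixture models are also listed.

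Four other places bear on the point:

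- Section 13.3: "Accounting for up to 20% drop-out, power calculations are based on 78 participants".
- Section 13.4: "Randomization will be blocked on stage (stages II-IIIA vs. IIIB-IV) and body mass index" (cut at 30 kg/m²).
- Sections 13.5 and 13.7 reuse the model: "We will use the above GEE model in this investigation to compare the mean changes" for norepinephrine, and "we will apply the GEE models for the primary analysis given above" for the subgroups.
- Section 13.6, on covariates, gives descriptive summaries and a check: "We will examine if covariates are balanced between study groups". It names no covariate for the model.

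**The concern.** Z_i carries no time index and the model has no Z-by-time term. Such a covariate shifts a participant's baseline and week-24 means by the same amount, so it explains level and not change. Because β1 is a contrast of changes, adding Z should leave it almost where it was.

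Two things are then at stake. A reader who sees unadjusted and adjusted results side by side will tend to take their agreement as evidence of robustness, although the model form makes that agreement nearly automatic. And the trial stratifies on stage and BMI but has no prespecified analysis in which the strata act on the treatment effect. BMI is offered only as an example covariate and stage is not mentioned, so the covariates could be chosen after the data are seen.

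**Working it through.** **1. Reproduce the plan's figure.** Inputs from Section 13.3: 39 per arm, two-sided type I error 0.05/7, 80% power, SF-36 physical component SD 9.2, ρ = 0.5, 0.65, 0.8.

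Detectable difference = (z[1 − 0.05/14] + z[0.80]) × SD × √(2(1 − ρ)) × √(2/39), with 2.690 + 0.842 = 3.532 and √(2/39) = 0.2265.

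- ρ = 0.5: 3.532 × 9.2 × 1.000 × 0.2265 = 7.36
- ρ = 0.65: 3.532 × 9.2 × 0.837 × 0.2265 = 6.16
- ρ = 0.8: 3.532 × 9.2 × 0.632 × 0.2265 = 4.65

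These match Table 1, so the power calculation rests on the unadjusted change contrast.

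**2. Algebra for a participant with both visits.**

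E[Y_i1 − Y_i0] = (α0 + α1 + β0 X_i + β1 X_i + γ'Z_i) − (α0 + β0 X_i + γ'Z_i) = α1 + β1 X_i.

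γ'Z_i is gone. This needs no assumption about how strongly Z predicts the outcome.

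**3. Numerical check on complete pairs.** Stated model, exchangeable working correlation, robust standard error, 78 simulated pairs:

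| Model | β1 | Robust SE |
|---|---|---|
| No Z | 5.765 | 1.827 |
| Z as main effects | 5.765 | 1.827 |
| Z-by-visit terms | 5.470 | 1.911 |

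A separate simulated dataset of 98 complete pairs gave −3.0555 (SE 1.5248) with no Z, with age and BMI, and with stage added, equal to the raw difference in mean change. Naming stage as a main effect would therefore not repair the model.

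**4. Planned size with missing visits.** Inputs: 49 per arm, 20 of 98 with baseline only, SD 9.2, the three ρ values, and an effect of 3.8 (Section 2.3: 1.8 against −2.0 in the earlier exercise trial). Assumption not in the documents: Z explains 5–20% of outcome variance. Effect of adding main-effect Z:

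| Dropout | Mean shift in β1 |
|---|---|
| Random | 0.03–0.10 SE (95th percentile 0.10–0.25) |
| Depends on Z alike in both arms | 0.04–0.11 SE |
| Depends on Z in opposite directions by arm | 0.14–0.42 SE |

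The ratio of adjusted to unadjusted SE was 0.991–1.001 throughout. With Z assumed to explain 30% of variance (ρ = 0.65), random dropout moved β1 by 0.18 points on average, about 0.10 SE, and the mean SE went from 1.692 to 1.677.

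**5. Imputed or carried-forward data.** Each participant again has two values, so the identity returns within each completed dataset. Simulated examples gave 3.4326 (SE 1.5245) for last observation carried forward and 4.8332 (SE 1.7406) for one regression imputation, each the same with and without Z.

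**6. Conditioning on the baseline outcome.** With equal variance at both visits, the ANCOVA variance is proportional to 1 − ρ² and the change-score variance to 2(1 − ρ). The SE ratio is √((1 + ρ)/2) = 0.866, 0.908 and 0.949. Applied to step 1 before rounding, this gives 6.37, 5.59 and 4.41.

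**The case against.** The strongest reply is that little inferential harm follows. The unadjusted contrast is valid under randomisation with complete data, comes first in the plan, and is what Table 1 powers. Section 13.2 never calls the adjusted result a robustness check. All of that stands, and it limits the weight of the point.

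Second, the quantified gain comes from the baseline outcome and not from age, BMI or stage, and Z-by-visit terms alone may gain nothing. This also stands. In the example above they raised the SE from 1.827 to 1.911. In a further simulation of 78 complete pairs (ρ = 0.65), the SE ratio to unadjusted was 1.02, 1.01, 0.99 and 0.91 for assumed age effects on change of 0, 1, 2 and 4 points per SD of age. The documents do not say which is realistic.

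Third, main-effect Z is not idle when visits are missing. With opposite-direction dropout by arm it removed bias (for example 4.18 to 3.76 against a true 3.8), and under an independence working correlation the shift can reach about 0.5 SE. These are real exceptions, but the first is an extreme mechanism and the second departs from the within-person correlation that Section 13.2 states. Endpoints with more single-visit data, such as norepinephrine, where remote participants skip urine collection, could also shift more than the simulations show. The weighted and pattern-mixture analyses were not simulated.

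Fourth, the covariate list is illustrative, so stage is unnamed and not excluded. That is correct, but a list that can still grow is not a prespecified one.

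**Conclusion.** The concern holds. For participants with both visits, the adjusted β1 and its robust standard error equal the unadjusted ones exactly. Across the planned trial the two analyses differ only through participants with one visit: about 0.03–0.10 SE on average under random dropout, with under 1% change in precision, given exchangeable correlation and Z explaining 5–20% of variance. The near-equality should not be extended to strongly arm-differential dropout or to an independence working correlation. Stage is named in no model. The primary contrast is not invalid and the stated power is unaffected. The defect is that a promised adjustment does not do what the plan says. It should be corrected, but it does not threaten the trial's validity.

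**What to change.** Prespecify one primary analysis per endpoint that adjusts the change.

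- **Option (a), preferred:** ANCOVA of the week-24 value on baseline outcome, arm, stage stratum (II–IIIA vs IIIB–IV), BMI stratum (<30 vs ≥30 kg/m²) and age. This brings the gain in step 6. It drops participants without a week-24 value unless they are imputed, so state which of the Section 13.2 missing-data methods applies.
- **Option (b):** keep the longitudinal model and enter stage stratum, BMI stratum and age as covariate-by-visit terms. This retains participants with one visit, but the documents support no claim of a precision gain.

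List the covariates in full in Section 13.6 in place of the open examples, apply the same model in Sections 13.5 and 13.7, and report the unadjusted change contrast as supportive.

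The cost is a few degrees of freedom and a change of text. Because the protocol is at version 8.0 with participants already enrolled, the change should be a documented amendment made before outcome data are examined by arm. No new data are needed: stage and BMI category are required to randomise, age and the baseline outcomes are collected, and Section 8.1 keeps BMI obtainable for remote participants from home weight and recorded or self-reported height. The Table 1 figures can stand.
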